***REAGIR: Corneal Cross-Linking with Rose Bengal***

Participants in Groups 4 and 5 will begin topical antimicrobial at enrollment.

Participants in Group 5 will receive RB-PDT and Group 4 will receive sham RB-PDT within 48 hours of randomization. Group 5 participants will receive a 30-minute loading dose of topical Rose Bengal (0.1% RB in 0.9% sodium chloride) which will be applied in 3-minute intervals to the de-epithelialized cornea. This will be followed by irradiation with a 6mW/cm^2 custom-made green LED source for 15 minutes (5.4J/cm^2). Participants in Group 4 will undergo a sham procedure using topical balanced salt solution and pen light covered with a green filter. Participants in both groups will undergo repeat cornea cultures within 24 hours after the procedure.

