#### 9.4.2 ANALYSIS OF THE SECONDARY ENDPOINTS

**Microbiological cure.** Studies have suggested that in addition to providing an initial diagnosis, repeated culture can be used to assess response to treatment and is highly correlated with clinical outcomes such as visual acuity. We will re-culture all study participants at Day 2, prior to starting antibiotics to assess the effect of CXL on rate of microbiological cure. We hypothesize that those in the CXL group (Group 3) will have a higher rate of microbiological cure on Day 2 cultures than those randomized to the Standard Therapy (Group 1) or Early Steroid Group (Group 2). Participants in both group 1 & 2 will serve as the comparison group increasing the power in this analysis.

We propose the primary analysis to be a Fisher's exact test comparing the proportion of positivity at follow-up between initially culture positive individuals who were assigned to cross linking (Group 3) versus initially culture positive individuals assigned to sham cross linking (Groups 1 and 2). Additionally, we will report the results for initially culture negative individuals as a supplementary analysis in a logistic regression with assignment, indicators for site (randomization strata), and initial culture results as covariates.

**Scar/infiltrate.** The analysis for scar/infiltrate size will follow the templates for visual acuity given above. Multiple linear regression models will be used to evaluate 12-month scar size by treatment arm (a 3-level categorical variable) while correcting for baseline measurements. As in the primary analysis, In SCUT II (groups 1, 2, 3) we will perform pairwise comparisons between arms with a significance level of  $0.05/2=0.025$ . In REAGIR (groups 4, 5) we will compare the two arms with significance level of 0.05. Corneal thinning and scarring will be evaluated similarly using Anterior Segment Optical Coherence Tomography (AS-OCT) correcting for baseline values.

**Corneal Perforation.** A Cox proportional hazards model will estimate the hazard of perforation, defined as perforation (flat anterior chamber with presence of iris plugging a defect in the cornea or seidel positivity) or the need for TPK while correcting for baseline infiltrate depth.

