3.1. Trial design

REAGIR is a multi-site, individually randomized, placebo-controlled trial. Patients presenting to one of the Aravind Eye Hospitals in India or to the University of California, San Francisco (UCSF) will be eligible for inclusion if they meet eligibility criteria (SAP section 5.2).

Enrolled participants will be randomized with equal probability (1:1) to one of two groups:

- **Sham RB-PDT:** Chlorhexidine gluconate, 0.02% (acanthamoeba), moxifloxacin 0.5% (smear/culture negative) or natamycin 5% (fungal keratitis) plus sham RB-PDT

- **RB-PDT**: Chlorhexidine gluconate, 0.02% (acanthamoeba), moxifloxacin 0.5% (smear/culture negative) or natamycin 5% (fungal keratitis) plus RB-PDT

Study participants will be required to have 8 visits: enrollment/baseline (Day 0), Day 1 (visit window: Day 1 or Day 2) for further assessments and to begin study drug, Day 2 for the cross-linking procedure within 48 hours of enrollment, and follow-up visits at 3 days, 3 weeks (visit window: 2.5 – 5 weeks), 3 months (visit window: 2.5 -3.5 months), 6 months (visit window: 5-7 months) and 12 months (visit window: 10-14 months). Additional visits may be needed and will be determined by the physician/investigator.

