Futility. Early discontinuation due to the unlikelihood of significant findings conditional on interim results may be considered, based on the original sample size considerations. For evaluating futility, we propose discontinuation for futility if the conditional power to detect a one line *benefit* drops below 20% at the interim analysis [2]. Conditional power will be derived by simulation of the unobserved future patients according to the original alternative hypothesis. Our proposed futility guidance is one-sided, and is subordinate to efficacy analyses.

Harm. Stopping for harm will be done at the judgment of the DSMC. Several endpoints will be examined, including (a) the best spectacle-corrected visual acuity at six months, (b) adverse events, and especially (c) serious adverse events, including corneal perforation or mortality. While the analysis would consider unbalanced distribution of predictive factors such as (a) infiltrate/scar size at presentation, (b) organism, and (c) repeat culture status, it is recognized that ethical considerations require careful considerations of statistical tests as well as qualitative judgments in the light of experience.

All subjects who provide informed consent will be accounted for in this study. We will present the number lost to follow-up and the number of protocol deviations by arm. The proportion of

subjects reporting adverse events and serious adverse events will be reported by arm to the DSMC and will be compared using a Fisher's Exact Test.

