6.1. Outcome definitions

Primary Outcome:

Best spectacle-corrected visual acuity measured in logMAR, 6 month follow-up visit

Secondary Outcomes:

- Microbiological cure on repeat smear and culture at Day 2
- Interaction of minimum inhibitory concentration (MIC) and CXL on best spectacle-corrected visual acuity
- Infiltrate/scar size/depth, as measured by clinical exam, clinical photographs, Pentacam and OCT at week 3 and months 3, 6, and 12
- Adverse events including rate of perforation/need for TPK
- BSCVA at Day 1, 3 weeks, 3 months, and 12 months
- Astigmatism, higher order aberrations, topography, and densitometry as measured on Pentacam at week 3 and months 3, 6, and 12
- Corneal thickness and scar size/depth as measured by AS-OCT at week 3 and months 3, 6, and 12
- Basal nerve plexus, white blood cell count, and keratocyte density on confocal microscopy at week 3 and months 3, 6, and 12

- Visual function questionnaire (VFQ) will be compared between groups at 6 months, controlling for Day 1 VFQ
- Pain scale at baseline, Day 1, and Day 3
- Subgroup analysis of study participants receiving prior topical antimicrobial therapy

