6.2. Analysis methods

Primary Outcome

Visual Acuity at 6 months. We will use a multiple linear regression model to estimate the mean difference between groups in BSCVA measured in logMAR at 6 months. The model will include covariates for treatment arm (a binary indicator variable for RB-PDT), indicators for study site (randomization strata), and baseline pinhole visual acuity. We propose a two-sided alpha of 0.05 for the primary analysis.

For study participants who experience perforation or the need for TPK this will be noted and BSCVA will be recorded prior to performing surgery (either corneal glue or TPK). These study participants actual 6-month visual acuity will be used in the primary analysis. As a sensitivity analysis, the last observation (at 3 weeks or 3 months) will be carried forward (LOCF) as the 6-month BSCVA.

The measurement window for the 6-month primary BSCVA outcome will be 5-9 months. The window was chosen after examining the distribution of measurement timing in masked data. As a sensitivity analysis, we will include all participants, including those who had their primary outcome measured out-of-window.

A supplementary analysis using linear mixed effects regression will be conducted to analyze all BSCVA data (including 3-week and 3-month observations). The model will include baseline BSCVA and treatment assignment as covariates (fixed effects) plus a random effect for patient to allow for repeated measures over time. Such analyses will be sharply distinguished from the primary pre-specified analysis. Permutation testing will be the basis of inference. Specifically, we will conduct 10,000 random permutations of treatment assignment, and conduct the primary regression analysis on these re-randomized data sets. We will then compare the observed regression coefficients to the randomization distribution, reporting the quantiles.

In all analyses, model adequacy will be checked by examination of residuals or other goodness of fit tests as needed. Inadequate model fit will prompt us to report alternative models. If there are chance imbalances in prognostic baseline patient characteristics, a secondary analysis will include them as covariates in the regression model.

Secondary Outcomes

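### The REAGIR harm guidance (SAP 3.5) lists repeat culture status, an outcome measured after RB-PDT, among the factors whose imbalance the harm analysis would consider

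*SAP*

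**What the plan says.** SAP 3.5 sets no numeric boundary for harm: "Stopping for harm will be done at the judgment of the DSMC". It then names what will be looked at: "Several endpoints will be examined, including (a) the best spectacle-corrected visual acuity at six months, (b) adverse events, and especially (c) serious adverse events", with corneal perforation and mortality given as examples of the last. It adds that the analysis would consider "unbalanced distribution of predictive factors such as (a) infiltrate/scar size at presentation, (b) organism, and (c) repeat culture status", and that ethical considerations call for statistical tests and qualitative judgment together. The closing paragraph of the section has the proportions with adverse and serious adverse events reported to the DSMC by arm and compared by Fisher's exact test.

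Elsewhere, SAP 6.1 lists "Microbiological cure on repeat smear and culture at Day 2" as a secondary outcome. Protocol 9.4.3 says DSMC reports will list study outcomes, microbiological ones included.

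**The concern.** Of the three named factors, infiltrate/scar size at presentation is fixed before treatment, and so is organism if it comes from the baseline work-up. An imbalance in either is due to chance, and it is reasonable to ask whether it explains a harm signal. Repeat culture status is different in kind. If RB-PDT changes it, an imbalance is part of what RB-PDT did, and allowing for it subtracts that part from the comparison.

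Two errors are possible. If RB-PDT leaves more eyes infected and they do worse, the excess can be put down to an imbalance in cultures. If RB-PDT clears cultures, comparing eyes with the same culture result can show harm where there is none overall.

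Perforation is a realistic worry in this field. Protocol 2.2 describes a small UVX trial in deep fungal ulcers that stopped after 13 patients over concern about perforation, although UVX is a different modality from RB-PDT. With no boundary for harm, the named factors are part of what guides the committee's judgment.

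**Working it through.** **Is repeat culture a baseline factor?**

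1. Procedure: SAP 3.1 reserves "Day 2 for the cross-linking procedure within 48 hours of enrollment".
2. Culture: Protocol 6.1.1 (REAGIR) says "Participants in both groups will undergo repeat cornea cultures within 24 hours after the procedure". The synopsis and the footnote to the schedule (Protocol 1.3) agree on the 24-hour timing for Groups 4 and 5. The schedule has smear/culture only at Day 0 and Day 2, so item (c) cannot be a pre-treatment culture.
3. Status: besides SAP 6.1, Protocol section 3 makes the effect of RB-PDT on microbiological cure a Specific Aim 4 objective, and SAP 6.2 expects a higher cure rate with RB-PDT.
4. Link to the harm endpoints: Protocol 9.4.2, in text built around the SCUT II groups, says "repeated culture can be used to assess response to treatment and is highly correlated with clinical outcomes such as visual acuity".

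Repeat culture therefore comes after treatment, is expected to respond to it, and is tied to outcome.

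**Plan figures.** No figure in the plan covers this point and none is disputed. The one plan figure used below reproduces: residual SD = 0.293 × √(1 − 0.216²) = 0.286. With 165 × 0.85 = 140.25 per arm, a difference of 0.11 and two-sided alpha 0.05, power is 0.896 against the stated 90%.

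**Perforation/TPK risk. All rates are assumptions.** Let p1 and p0 be culture positivity on RB-PDT and sham, R+ and R− the risk with a positive and a negative culture, and d any direct effect of RB-PDT.

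- Crude difference = (p1 − p0)(R+ − R−) + d
- Difference within culture strata = d
- Shift from stratifying = (p1 − p0)(R+ − R−)

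Take R+ = 0.50 and R− = 0.20.

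- *Harm masked* (p1 = 0.6, p0 = 0.3, d = 0): RB-PDT 0.6×0.50 + 0.4×0.20 = 0.38; sham 0.3×0.50 + 0.7×0.20 = 0.29. Crude +9 points; stratified 0.
- *Harm created* (p1 = 0.3, p0 = 0.6, d = 0.09): RB-PDT 0.29 + 0.09 = 0.38; sham 0.38. Crude 0; stratified +9 points.
- *Range*: 0.1 × 0.1 = 1 point; 0.3 × 0.3 = 9 points. With 50 per arm that is 0.5 to 4.5 events.

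**Selection, with no effect of RB-PDT on perforation.** Assume half the eyes are severe, perforation risk is 0.4 if severe and 0.1 if not, sham positivity is 0.7 and 0.3, and RB-PDT halves positivity.

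- Culture positive: risk 0.31 in both arms.
- Culture negative: RB-PDT 0.1725/0.75 = 0.23; sham 0.095/0.50 = 0.19.
- Mantel-Haenszel weights 0.167 and 0.300: (0.300 × 0.04)/0.467 = +2.6 points, against a true 0.

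Cutting positivity by 25% or 75% instead gives +1.4 or +3.9 points.

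**BSCVA at the 100-participant interim.** Simulation with 50 per arm, SD 0.286 and 4,000 runs. Higher logMAR is worse, and a signal is a test statistic above 1.96 in the harm direction. In the first two rows a positive culture is assumed to cost 0.4 logMAR. In the last three, culture and treatment have no effect, and unmeasured severity drives both culture and acuity.

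| Positivity, sham to RB-PDT | Difference, unadjusted | Difference, adjusted for culture | Signal, unadjusted | Signal, adjusted |
|---|---|---|---|---|
| 40% to 70% | 0.118 | −0.002 | 41% | 2.2% |
| 40% to 60% | 0.079 | −0.001 | 21% | 2.6% |
| 60% to 30% | 0.001 | 0.045 | 2.9% | 12% |
| 60% to 20% (stronger severity link) | −0.001 | 0.093 | 2.5% | 35% |
| 40% to 20% | 0.000 | 0.030 | 2.7% | 7.9% |

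**The case against.** The best reply is that the text plans no adjustment. It speaks of considering imbalance, in a subordinate clause of a sentence whose weight falls on careful judgment, and it fixes no model, stratification or discount. A DSMC that includes cornea specialists and an independent biostatistician (Protocol 10.1.6) might look at culture imbalance to ask how harm arises. This stands: the distortion is a risk, not a planned analysis.

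A reader might infer that this list is the only harm guidance for REAGIR. It is not. SAP 3.5 itself gives the DSMC an unadjusted comparison of adverse and serious adverse events by arm, and SAP 6.5 repeats Fisher's test. Protocol 8.3.5 and 8.3.6 add twice-yearly review of adverse events and monthly reports of serious ocular events, with TPK and perforation among the examples. A crude excess of perforations would be in view. That safeguard does not extend to BSCVA, the first endpoint named under Harm. The SAP 6.2 primary model omits repeat culture, but the Harm paragraph does not say that model is to be used.

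A reader might also infer that SAP 6.2 already forbids the practice, since it begins its imbalance rule with "If there are chance imbalances in prognostic baseline patient characteristics". That rule prompts a secondary efficacy analysis. It states no prohibition and does not govern DSMC review. It shows only that the plan elsewhere thinks of imbalance in baseline terms.

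Finally, the 9-point cases are strong ones. Masking 9 points needs RB-PDT to double positivity, the reverse of the hypothesis, and REAGIR's smear- and culture-negative ulcers would be expected to dilute any arm difference in positivity. Both objections are fair.

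**Conclusion.** The point holds as a wording fault with a real but unquantified consequence. Repeat culture status does not belong among factors whose imbalance may qualify a harm signal, because in REAGIR it is measured after RB-PDT/sham and is an outcome of it. The direction of error depends on what RB-PDT does: harm is masked if positivity rises, and apparent harm can be created if it falls as hypothesised.

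The range of about 1 to 9 percentage points, and the BSCVA shifts, rest on assumed culture and event rates and on full adjustment for culture. They show what could happen and do not estimate what will. The documents do not support a claim that the DSMC is told to discount harm, or that it would see only adjusted results. The other two listed factors, the primary model, the Fisher comparison and the sample size are unaffected.

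**What to change.** In SAP 3.5 (Harm):

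- Delete item (c).
- Limit the factors considered for imbalance to those measured before RB-PDT/sham, for example infiltrate/scar size at presentation and organism from the baseline work-up. Putting baseline smear/culture in place of (c) is unnecessary, since it largely repeats organism.
- State that repeat culture is shown to the DSMC by arm as an outcome. Protocol 9.4.3 already puts microbiological outcomes in the DSMC reports, so this only adds the split by arm and the label.

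The cost is a line or two in the SAP and the DSMC report template. The committee loses no information, and no data collection, alpha or sample size changes.

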3.6. Timing of the final analysis

The primary analysis will commence after all enrolled patients complete their 6-month outcome assessment (or would have completed their 6-month assessment, if lost to follow-up).

3.7. Timing of outcome assessments

Protocol section 1.3 includes a detailed measurement schedule for the trial. Participant BSCVA will be measured at enrollment, and at 3-months, 6-months, and 12-months following treatment. The 6-month measurement is the primary outcome. Measurements at 3-months and 12-months are secondary outcomes.

4. Statistical Principles

4.1. Confidence intervals and *P*-values

We will test for difference between arms in the primary outcome (BSCVA at 6 months follow-up) using a $p=0.05$ level to assess statistical significance. We will construct two-sided 95% confidence intervals to test for superiority of RB-PDT versus sham.

We will report 95% confidence intervals on our measures of effect (difference in BSCVA logMAR) on each secondary outcome. We do not plan to adjust secondary outcome confidence intervals for multiplicity because we expect them to be highly correlated and together they provide corroborating evidence for or against the primary outcome hypothesis.[3]

4.2. Protocol deviations

The analysis population will be intention to treat, and will include all participants enrolled and randomized. Adherence to protocol will be assessed in the hospital for the first 3 days with observed administration of the treatment. Later compliance will be assessed by questioning the patient and collecting empty bottles over the entire treatment duration. The trial will assess whether patients adhered to the treatment regimen: Chlorhexidine gluconate, 0.02% (acanthamoeba), moxifloxacin 0.5% (smear/culture negative) or natamycin 5% (fungal keratitis), plus RB-PDT or sham RB-PDT depending on the group. Patients who deviate from protocol will be included according to randomized group in the intention-to-treat analysis.

5. Trial Population

5.1. Screening data

We will report the number of patients screened by study side and characteristics to the extent they are available to assess representativeness of the enrolled study population.

5.2. Eligibility

Participants who are screened will be eligible to enroll in the trial if they meet these criteria:

- either smear or culture positive fungal, or
- acanthamoeba keratitis, or
- smear and culture negative corneal ulcers and moderate to severe vision loss, defined as Snellen visual acuity of 20/40 or worse

5.3. Recruitment

The trial will report the number of participants screened, eligible to enroll, randomized, and measured at each trial visit (Protocol section 1.3 includes details about each planned visit). The trial will report recruitment progress at regular DSMC meetings to monitor trial progress.

5.4. Withdrawal/follow-up

We will report the number and proportion of patients in both study arms who withdraw from the trial, along with reasons. We will report this information in the trial's CONSORT flow chart, summarizing losses to follow-up at each trial visit (3 months, 6 months, 12 months). The analysis will be intention-to-treat: patients will be analyzed according to the arm they are randomized.

5.5. Baseline patient characteristics

We will summarize trial participant age, sex, occupation, medication use at enrollment, eye trauma, and clinical characteristics at enrollment, including medication use at enrollment, trauma, affected eye, visual acuity, infiltrate and/or scar size, hypopyon, depth, epithelial defect, duration of symptoms, and systemic disease. We will summarize means (or proportions for binary variables) by treatment group, along with standard deviations for quantitative variables.

6. Analysis

6.1. Outcome definitions

Primary Outcome:

Best spectacle-corrected visual acuity measured in logMAR, 6 month follow-up visit

Secondary Outcomes:

- Microbiological cure on repeat smear and culture at Day 2
- Interaction of minimum inhibitory concentration (MIC) and CXL on best spectacle-corrected visual acuity
- Infiltrate/scar size/depth, as measured by clinical exam, clinical photographs, Pentacam and OCT at week 3 and months 3, 6, and 12
- Adverse events including rate of perforation/need for TPK
- BSCVA at Day 1, 3 weeks, 3 months, and 12 months
- Astigmatism, higher order aberrations, topography, and densitometry as measured on Pentacam at week 3 and months 3, 6, and 12
- Corneal thickness and scar size/depth as measured by AS-OCT at week 3 and months 3, 6, and 12
- Basal nerve plexus, white blood cell count, and keratocyte density on confocal microscopy at week 3 and months 3, 6, and 12

- Visual function questionnaire (VFQ) will be compared between groups at 6 months, controlling for Day 1 VFQ
- Pain scale at baseline, Day 1, and Day 3
- Subgroup analysis of study participants receiving prior topical antimicrobial therapy

6.2. Analysis methods

Primary Outcome

Visual Acuity at 6 months. We will use a multiple linear regression model to estimate the mean difference between groups in BSCVA measured in logMAR at 6 months. The model will include covariates for treatment arm (a binary indicator variable for RB-PDT), indicators for study site (randomization strata), and baseline pinhole visual acuity. We propose a two-sided alpha of 0.05 for the primary analysis.

For study participants who experience perforation or the need for TPK this will be noted and BSCVA will be recorded prior to performing surgery (either corneal glue or TPK). These study participants actual 6-month visual acuity will be used in the primary analysis. As a sensitivity analysis, the last observation (at 3 weeks or 3 months) will be carried forward (LOCF) as the 6-month BSCVA.

The measurement window for the 6-month primary BSCVA outcome will be 5-9 months. The window was chosen after examining the distribution of measurement timing in masked data. As a sensitivity analysis, we will include all participants, including those who had their primary outcome measured out-of-window.

A supplementary analysis using linear mixed effects regression will be conducted to analyze all BSCVA data (including 3-week and 3-month observations). The model will include baseline BSCVA and treatment assignment as covariates (fixed effects) plus a random effect for patient to allow for repeated measures over time. Such analyses will be sharply distinguished from the primary pre-specified analysis. Permutation testing will be the basis of inference. Specifically, we will conduct 10,000 random permutations of treatment assignment, and conduct the primary regression analysis on these re-randomized data sets. We will then compare the observed regression coefficients to the randomization distribution, reporting the quantiles.

In all analyses, model adequacy will be checked by examination of residuals or other goodness of fit tests as needed. Inadequate model fit will prompt us to report alternative models. If there are chance imbalances in prognostic baseline patient characteristics, a secondary analysis will include them as covariates in the regression model.

Secondary Outcomes

Visual Acuity at 3 weeks, 3 months, and 12 months. We will compare BSCVA between arms at 3 weeks, 3 months, and 12 months follow-up using the same approach as the primary analysis. We will only complete this analysis after the primary analysis is complete and the trial is unmasked.

Scar/infiltrate. The analysis for scar/infiltrate size will follow the templates for visual acuity given

above. Multiple linear regression models will be used to evaluate 3-week, 3-month, 6-month, and 12-month scar size by treatment arm while correcting for baseline measurements. Corneal thinning and scarring will be evaluated similarly using Anterior Segment Optical Coherence Tomography (AS-OCT) correcting for baseline values.

Corneal Perforation. A Cox proportional hazards model will estimate the hazard of perforation, defined as perforation (flat anterior chamber with presence of iris plugging a defect in the cornea or seidel positivity) or the need for TPK while correcting for baseline infiltrate depth.

Microbiological cure. We will re-culture all study participants at Day 2, prior to starting antibiotics to assess the effect of RB-PDT on rate of microbiological cure. We hypothesize that those in the RB-PDT group (Arm 2) will have a higher rate of microbiological cure on 2 day cultures than those randomized to the Sham group (Arm 1).

We propose the primary analysis to be a Fisher's exact test comparing the proportion of positivity at follow-up between initially culture positive individuals who were assigned to RB-PDT (Arm 1) versus initially culture positive individuals assigned to the Sham group (Arm 1).

Additionally, we will report the results for initially culture negative individuals as a supplementary analysis in a linear binomial regression with assignment, indicators for site (randomization strata), and initial culture results as covariates.

Visual Function Questionnaire (VFQ). VFQ will be compared between arms controlling for Day 1 VFQ. NEI-VFQ in the US and the Indian-VFQ (IND-VFQ) in India. This will be conducted using linear regression with baseline and treatment assignment variables.

Pain Scale. Pain is assessed at day 0, day 1, and day 3 using a 0-10 scale for patient self-assessment. Multiple linear regression models will be used to evaluate 3-day pain by treatment arm while correcting for baseline pain.

Minimum Inhibitory Concentration (MIC). The analysis of MIC will follow the primary analysis but include an interaction of minimum inhibitory concentration (MIC) and RB-PDT on best spectacle-corrected visual acuity.

Pre-specified Subgroup Analyses

The trial has two planned subgroup analyses. The first subgroup analysis will stratify the analysis by infectious organism: fungal, acanthamoeba, or smear and culture negative. If patients are smear negative and are suspected fungal or acanthamoeba, we will use confocal microscopy to determine the patient's subgroup. The second subgroup analysis will stratify patients by whether they had received prior topical anti-microbial therapy at enrollment. In both cases, we will add indicator variables for subgroups to the linear regression model plus interaction terms between indicator variables and the treatment arm. We will test for interaction on the additive scale based on coefficients on the interaction terms in the models. Ulcer depth is thought to be a strong determinant of outcomes among patients with acanthamoeba infections. The infectious organism subgroup analysis will include ulcer depth as an additional covariate in the model to potentially improve precision.

